#### 9.4.7 EXPLORATORY ANALYSES

The PI will evaluate the feasibility of several potential exploratory analyses methods and proceed with analyses. The following exploratory analyses methods are considered to investigate the utility of improved CBCT image quality. After the completion of research CBCT scans, the PI will consult with the study team to identify the final exploratory analyses methods. Several example exploratory analyses are: 1) We will evaluate the consistency of organ delineation across participants and different observers. We will involve calculating the intra-class correlation coefficient (ICC), a reliability metric, for standard clinical CBCT and research CBCT. The ICC is simply the proportion of the total variability in the data that can be attributed to variability between

participants. In the context of this study, the ICC is directly related to how well the observer delineations agree, with a higher ICC indicating better agreement. For example, an ICC of 0.8 would indicate that 80% of the variance is due to differences between participants, while 20% of the error is due to differences among observers (i.e., within-participant variability) or measurement error. We hypothesize that the agreement among clinicians will be better (i.e., higher ICC) for the research CBCT compared to the standard clinical CBCT. For each patient, the Conformity Index (CI) and Hausdorff distance (HD) will be calculated and used as similarity metrics to calculate and compare ICCs between the imaging modalities as defined below.

For each participant and CBCT modality an average delineation will be determined using the STAPLE algorithm. This average delineation will be used as the reference delineation to compute four pairwise CIs between the reference and each observer. This pairwise approach to determine the CIs was chosen over the generalized conformity index since it can be used to account for variability among the observers, which in turn will improve our ability to compare the two imaging modalities. A two-way random effects model (random effects for participant and observer) will be carried out for each modality to calculate the ICC and its 95% confidence interval using bootstrapping for absolute agreement. The ICC will be calculated using the form ICC(2,k) so that the results can be generalized to any observer with a similar skill set. If the 95% confidence interval of ICC does not overlap between the two modalities, we will conclude they are significantly different at a 0.05 significant level. We will also examine whether anatomical location impacts performance through subgroup analyses on Groups 1-3.

2) The consistency and reproducibility of radiomics features (image texture and intensity features) in CBCT images will be analyzed. Some examples of radiomics features are mean, standard deviation, kurtosis of pixel value histograms, Gray Level Co-occurrence Matrix (GLCM), Gray Tone Difference Matrix (GTDM), and Spatial Correlation of pixel values. Up to 50 prominent radiomics features will be selected using a similar approach as described by Fave et al. [36] and Zhao et al. [35]. Subsequently, correlation of these radiomics features extracted from research and standard clinical CBCT scans will be measured with respect to radiomics features extracted from MDCT scans for all participants and for each subgroup, as listed in Section 9.4.6.1. 2) Qualitative improvement in image quality will be analyzed in an observer study. Standard clinical and research CBCT scans of study participants will be presented to observers in a blind fashion, and observers will rank the quality of images based on their clinical experience. 3) CBCT image quality will be evaluated using quantitative image quality metrics, such as CT number accuracy, contrast to noise ratio, and image noise. The difference in measured image quality metrics between the research and standard clinical CBCT scans will be evaluated. 4) Radiotherapy dose calculations will be performed by using standard clinical and research CBCT scans. Dose calculated with CBCT scans will be compared to the dose calculated with the gold standard MDCT scans by using dose volume histogram metrics. Dosimetric differences between each CBCT-MDCT dose pair will be analyzed. We hypothesize that dose calculated with research CBCT scans will have lower dosimetric errors than the dose calculated with standard clinical CBCT scans.

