## 9 STATISTICAL CONSIDERATIONS

### 9.1 STATISTICAL HYPOTHESES

- Primary Efficacy Endpoint:  
The primary endpoint of this study is to evaluate the change in objective image quality metrics in CBCT images acquired with the 2D grid, when compared to CBCT images without the 2D grid. We will place multiple ROIs in each CBCT scan, and calculate absolute CT number error, artifact amplitude, and contrast to noise ratio (CNR). We will evaluate the statistical significance of the differences of these metrics between research CBCT and standard clinical CBCT scans. We hypothesize that CBCT scan with 2D grid will provide significantly lower CT number errors and artifact amplitudes when compared to standard clinical CBCT scans. We also hypothesize that CBCT scans with 2D grid will provide equivalent or better CNR than standard clinical CBCT scans.
- Secondary Efficacy Endpoint(s):
  - 1) We hypothesize that the accuracy of software tools can also be improved in auto-delineation of tissues in CBCT scans. In this case, we will use manual delineations from the observers as the gold standard and measure the similarity of software generated and observer generated delineations by using the CI and HD metrics.

- Tertiary Efficacy Endpoint(s):
  - 1) Assessment of radiomics feature extraction accuracy: We hypothesize that image intensity and texture (radiomics) features are more consistent in higher quality CBCT images. The gold standard consistency of radiomics features is MDCT scans. Thus, we will evaluate the correlation of radiomics features in CBCT scans and MDCT scans, by using the CCC metric. Higher correlation of radiomics features between CBCT and MDCT scans will yield higher CCC values.
  - 2) Assessment of image quality rankings by observers, evaluation of quantitative image quality metrics, and evaluation of dose calculation accuracy. Metrics obtained in each study will be evaluated comparatively. The statistical significance of differences in quality metrics extracted from research and standard clinical CBCT scans will be evaluated.
  - 3) Determine the consistency of organ/tissue delineations across different observers, when using CBCT image sets with better image quality. We will calculate intra-class correlation coefficient (ICC) on CI and HD metrics to measure the effect of standard clinical CBCT and 2D Grid CBCT on organ delineation consistency.

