## 9.4 STATISTICAL ANALYSES

### 9.4.1 GENERAL APPROACH

**Study #1 (Primary objective):** Improvement in tissue visualization and quantitative accuracy will be evaluated comparatively between the CBCT scans acquired with and without the 2D grid. Objective image metrics will be employed to quantify tissue visualization and quantitative accuracy. Three image quality metrics will be extracted from each CBCT scan; absolute CT number error, image artifact amplitude, and contrast to noise ratio (CNR). To calculate CT number errors and artifact amplitude, multiple ROIs will be placed primarily in the soft tissue and adipose sections of the imaged anatomy in coregistered CBCT and simulation CT images. CT number error is defined as the absolute difference in mean HU values between the CBCT and the gold standard CT images of a given ROI. Artifact amplitude is defined as the difference between the maximum and minimum value of CT number errors extracted from ROIs in a given CBCT scan. For CNR calculations paired ROIs will be placed in each imaged volume, such that one of the ROIs in the pair will be placed in soft tissue, and the other will be placed in adipose tissue in proximity of the first ROI. CNR is calculated by using the following:

$$CNR = \frac{|HU_{soft} - HU_{adipose}|}{(\sigma_{soft} + \sigma_{adipose})/2}$$

Where  $HU_{soft}$  and  $HU_{adipose}$  are the mean HU values of soft tissue and adipose tissue ROI pairs.  $\sigma_{soft}$  and  $\sigma_{adipose}$  are the HU standard deviation of soft tissue and adipose tissue ROI pairs. These metrics serve as surrogates that quantify tissue visualization. A statistically significant improvement in these metrics when compared to metrics extracted from standard clinical CBCT scans would indicate that tissue visualization and quantitative accuracy would be potentially improved by CBCT scans with 2D grid.

**Study #2 (Secondary Objective), evaluate the consistency of organ delineation by automated software tools:** Evaluations in study 2 will be similar as those in study 1. The exception is that the pairwise comparisons will consist of comparing the automated software delineation to delineations for each of the four observers. This will allow us to evaluate how consistent the automated delineation is with human delineations, and whether a given imaging modality results in a more consistent automated delineation.

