#### **9.4.3 ANALYSIS OF THE SECONDARY ENDPOINT(S)**

The analysis of this endpoint will be conceptually similar to primary endpoint, but this time, we will evaluate the consistency of delineations performed by automated software tools, which can greatly improve workflow efficiency in CBCT-based treatment monitoring. We will employ Machine Learning-based organ delineation and evaluate its accuracy with respect to observer-delineated structures.

Workflow: 1) Both research and standard clinical CBCT scans will be registered to helical CT images. After registration, observer-delineated structures will be also delineated independently by Machine Learning Methods. 2) Machine Learning based delineations will be compared to observer-generated delineations in CBCT scans. 3) We will use the similarity (i.e. CI and HD) and reliability (i.e. ICC) metrics to assess the consistency between Machine Learning-based and observer-generated delineations. The Machine Learning model for delineation will be selected by the PI, based on the availability of models for anatomical structures delineated by the observer.

---

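### Exploratory observer analysis: the two CBCT types are compared through the ICC of CI and HD scores, which reflects spread between participants and can stay flat or fall when contours agree better

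*Combined protocol and SAP*

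**What the plan says.** **Observer analysis (exploratory).** Section 9.4.1, Study #3, has four blinded observers contour each scan and forms a STAPLE consensus. Section 9.4.7 will then "compute four pairwise CIs between the reference and each observer". Section 9.4.1 treats a CI of 1 or an HD of 0 mm as perfect agreement. Section 9.1 says: "We will calculate intra-class correlation coefficient (ICC) on CI and HD metrics to measure the effect of standard clinical CBCT and 2D Grid CBCT".

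Section 9.4.7 states that "the ICC is directly related to how well the observer delineations agree, with a higher ICC indicating better agreement". As illustration, "an ICC of 0.8 would indicate that 80% of the variance is due to differences between participants", with the remaining 20% put down to observers or measurement error. The direction of the hypothesis follows: "We hypothesize that the agreement among clinicians will be better (i.e., higher ICC) for the research CBCT". On the form: "The ICC will be calculated using the form ICC(2,k) so that the results can be generalized to any observer with a similar skill set". The two CBCT types are declared different at the 0.05 level if their 95% bootstrap intervals for the ICC do not overlap. For this analysis no test of mean CI or HD and no reporting of variance components is described.

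**Secondary analysis.** Section 3 defines the endpoint by similarity metrics, and section 9.1 names these as CI and HD. Section 9.4.3 adds ICC beside them: "We will use the similarity (i.e. CI and HD) and reliability (i.e. ICC) metrics to assess the consistency". It gives no ICC form, model or decision rule. Section 9.4.1 says only "Evaluations in study 2 will be similar as those in study 1".

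**Sample size.** Section 9.2 states its precision in terms of an ICC.

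**The concern.** Each CI or HD value is already a measure of how close a contour lies to the consensus. Sections 9.4.1 and 9.4.7 themselves define ICC as the share of total variability that lies between participants. Applied to these scores, ICC shows how well the scores separate one participant from another. It does not show how well the contours agree.

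The trial deliberately mixes sites and pelvis sizes, and section 4.1 says larger patients produce more scatter. If the grid helps the worst-imaged participants most (an inference, not a statement in the plan), scores become more alike across participants and the ICC can drop. A rule resting on ICC alone could then report better contouring as no change or as harm.

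**Working it through.** **1. The plan's own figure.** Section 9.2: 32 participants; reference ICC 0.95, 0.90 and 0.80; detectable increases 3.5%, 7.7% and 17%. I used the exact F interval for an average-measures, two-way ICC with k = 4 observers, so the degrees of freedom are 31 and 31 × 3 = 93:

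- lower limit = 1 − (1 − r) × F(0.975; 31, 93)
- upper limit = 1 − (1 − r) / F(0.975; 93, 31)

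The upper limits for the three reference values are 0.9733, 0.9465 and 0.8931. The smallest increases whose lower limit reaches them are 3.6%, 7.7% and 17.2%, all within 0.2 points of the plan. The statement is reproducible, although other forms come close (single-measure, k = 3: 3.7%, 7.7%, 16.9%). It describes how precisely an ICC is estimated, not whether ICC tracks agreement.

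**2. What enters the ICC.** Let Vp be the between-participant variance of the score and Vw the within-participant variance (observer plus residual).

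- ICC(2,1) = Vp / (Vp + Vw)
- ICC(2,k) = Vp / (Vp + Vw/k) = 1 / (1 + Vw/(k·Vp))

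Only the ratio Vw/Vp matters. The mean CI or HD does not appear. ICC falls whenever Vp shrinks proportionally more than Vw.

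**3. A fall with less observer spread.** The SDs of CI are assumed; the documents give none.

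| | SD between | SD within | Vw/Vp | ICC(2,1) | ICC(2,4) |
|---|---|---|---|---|---|
| Standard | 0.10 | 0.05 | 0.0025/0.0100 = 0.25 | 0.0100/0.0125 = 0.80 | 0.0100/0.010625 = 0.94 |
| Grid | 0.04 | 0.03 | 0.0009/0.0016 = 0.5625 | 0.0016/0.0025 = 0.64 | 0.0016/0.001825 = 0.88 |

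Within-participant variance falls by 64% and between-participant variance by 84%, so ICC falls.

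**4. A rise from heterogeneity alone.** With assumed participant, observer and residual SDs of 0.10, 0.02 and 0.05, Vw = 0.0004 + 0.0025 = 0.0029 and ICC(2,4) = 0.0100/0.010725 = 0.932. Doubling the participant SD to 0.20, with observers unchanged, gives 0.0400/0.040725 = 0.982. Halving the observer and residual SDs, with participants unchanged, gives the same 0.982. ICC cannot tell the two apart.

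**5. Contour-level simulation.** 32 participants, 4 observers, a median contour in place of STAPLE. The contour error and its between-participant spread (log-SD) are assumed.

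| Case | Error | Log-SD | Inter-observer CI | ICC(2,4) of CI |
|---|---|---|---|---|
| Standard | 4 mm | 0.5 | 0.716 | 0.88 |
| Standard, more mixed | 4 mm | 0.8 | 0.695 | 0.945 |
| Grid | 2 mm | 0.5 | 0.841 | 0.89 |
| Grid | 2 mm | 0.25 | 0.852 | 0.68 |
| Grid | 2 mm | 0.1 | 0.855 | 0.23 |

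Halving the error improves inter-observer CI in every grid row, while ICC stays flat or falls. Between the first and last rows, mean CI rises from 0.820 to 0.912 and mean HD falls from 9.7 to 4.3 mm. In that extreme pairing the non-overlap rule called the grid significantly worse in 195 of 200 simulated trials and better in none.

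**6. Form against interpretation.** Inverting step 2 with k = 4, ICC(2,1) = R / (4 − 3R), where R is ICC(2,4). For R = 0.80 this is 0.80/1.60 = 0.50, so half of the single-score variance lies between participants. The 80%/20% reading fits ICC(2,1) = 0.80, for which ICC(2,4) = 3.2/3.4 = 0.94.

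**The case against.** **The same participants are scanned both ways, so heterogeneity is held constant.** Their anatomy is. Vp, however, is the spread of agreement scores, which depends on image quality and can differ between the CBCT types.

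**The reversal is a chosen scenario.** This stands as a limit. All SDs are assumed, and a fall needs between-participant variance to shrink proportionally more than within-participant variance. With equal relative spread the simulated ICC barely moved (0.88 to 0.89). That is still a failure of the measure, since contour error had halved.

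**The analysis is exploratory and may never be run.** True: section 9.4.7 lists it among examples to be settled after scanning. This limits the weight of the point. It does not make the rule suitable if the analysis is run.

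**The secondary endpoint.** A reader might infer that the secondary endpoint could declare the grid worse while every participant's contours improved. The documents do not support that. Section 3 and section 9.1 define the endpoint by similarity, with CI and HD as the metrics, and section 9.4.3 only lists ICC beside them. Software contours uniformly far from all observers would show in CI and HD. Sections 9.4.1 and 9.4.3 also liken this analysis to the primary one, now a mixed model, which is close to the remedy below. What remains is that the role of ICC there is unstated.

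**ICC(2,k) against ICC(2,1).** A reader might infer that the mismatch distorts the comparison. At fixed k = 4, one is a strictly increasing function of the other, so the ordering of the two CBCT types is the same under either. Section 9.4.3 names no form, so the mismatch does not reach it.

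**Conclusion.** The concern holds for the exploratory observer analysis. Its only stated comparison rests on a quantity that ignores the mean score, rises with heterogeneity, and can stay flat or fall as contours improve. Under the assumed SDs, ICC(2,4) moves from 0.94 to 0.88 while observer spread shrinks. Across the simulated cases with contour error halved, it ends anywhere from 0.89 to 0.23 against a starting 0.88. The algebra needs no assumption; the sizes do, and how likely a reversal is cannot be judged from the documents.

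For the secondary analysis, only a clarification of the role of ICC is needed. The 80%/20% sentence is a wording error. The primary endpoint analysis in section 9.4.2 (CT number error, artifact amplitude, CNR) does not use ICC and is unaffected, although section 9.2 still ties an ICC statement to the primary hypothesis.

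**What to change.** - **Section 9.4.7 and section 9.4.1, Study #3:** compare the CI and HD values themselves. Use a mixed model with CBCT type fixed and participant and observer random, and report the paired research-minus-standard difference with its 95% confidence interval. Analyse HD on its original scale or with a transformation defined at 0 mm; a plain logarithm is not, and 0 mm is the plan's value for perfect agreement. Report the within-participant observer SD. Keep ICC as descriptive only and drop the non-overlap rule.
- **Section 9.4.3:** state that the secondary conclusion rests on the same direct CI and HD comparison, in line with sections 3 and 9.1, and not on ICC.
- **Section 9.4.7, wording:** attach the 80%/20% interpretation to ICC(2,1), or reword it for ICC(2,k).
- **Section 9.2:** relabel the precision statement as describing the descriptive ICC.

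The cost is plan wording, best settled before results are seen. Scans, contours and CI/HD scores stay the same. The downside is that section 9.2, the plan's only sample-size statement, would no longer support any inferential comparison.

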**Study #3 (Exploratory Objective), assess the utility of CBCT images in qualitative and quantitative imaging tasks:** Several studies will be considered for the exploratory analysis.

Improvement of organ or anatomical structure visualization by observers: We hypothesize that anatomical structure visualization can be improved by higher quality CBCT images. To quantify tissue visualization, we will ask multiple observers to delineate organ boundaries. Since the ground truth about organ boundaries cannot be determined from images, we will evaluate the inter-observer agreement among delineated structures. Four observers will delineate a set of anatomical

structures in each helical CT and CBCT scan in a blinded fashion. For each image set, a reference delineation will be determined from delineations of four observers using the STAPLE algorithm. Conformity Indexes (CI) and Hausdorff distances (HD) will be used as metrics of similarity. CI is the ratio of the sum of all overlapping volumes between pairs of observers and the sum of all overlapping and all non-overlapping volumes between the same pairs. HD defined as the maximum distance between the closest points of two delineations. CI of one or HD of 0 mm indicates perfect agreement among observers' delineations. We will have CIs and HDs determined between the reference delineation and each observer. This pairwise approach to determine the CIs can be used to account for variability among the observers, which in turn will improve our ability to compare the two imaging modalities.

To evaluate the consistency of organ delineation by different observers, we will calculate intraclass correlation coefficient (ICC), which is a reliability metric. The ICC is simply the proportion of the total variability in the data that can be attributed to variability between participants. In the context of this study, the ICC is directly related to how well the observer delineations agree, with a higher ICC indicating better agreement. Our aim is to evaluate how ICC varies between standard clinical CBCT and CBCT with 2D grid. We hypothesize that the ICC will be better for CBCT with 2D grid.

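### Exploratory observer study: each observer is scored against a STAPLE consensus that contains that observer's own contour, which overstates agreement and lowers the ICC used to compare the scan types

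*Combined protocol and SAP*

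**What the plan says.** Section 9.4.1 (Study #3) has four blinded observers contour each helical CT and CBCT scan. For each image set, "a reference delineation will be determined from delineations of four observers using the STAPLE algorithm". The scores follow from that reference: "We will have CIs and HDs determined between the reference delineation and each observer". Section 9.4.7 repeats this for each participant and CBCT type: "This average delineation will be used as the reference delineation to compute four pairwise CIs between the reference and each observer". No section builds the reference without the scored observer or uses an independent one.

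Section 9.4.7 then fits a two-way random-effects model (participant and observer) to the scores of each scan type and computes ICC(2,k) for absolute agreement with a bootstrap 95% interval. The scan types are declared different at the 0.05 level if the two intervals do not overlap. The plan's own gloss is: "The ICC is simply the proportion of the total variability in the data that can be attributed to variability between" participants.

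Two further statements matter. Section 9.4.1 also defines the index differently: "CI is the ratio of the sum of all overlapping volumes between pairs of observers" to the overlapping plus non-overlapping volumes of those pairs, with no consensus involved. And it defends the reference-based scores: "This pairwise approach to determine the CIs can be used to account for variability among the observers", and so sharpen the comparison of scan types. Section 9.4.7 shows that the alternative in mind is the generalized conformity index.

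**The concern.** A score against a consensus that includes one's own contour is a part-whole comparison. Each observer has already pulled the reference towards his or her own contour, so agreement looks better than it is on both scan types.

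STAPLE adds a second effect. It weights raters by their estimated sensitivity and specificity. With four raters, a 2-2 split is settled by those weights, so one or two raters can capture the reference and score almost perfectly while the others are marked down. This spread within a participant comes from the algorithm, and it enters the error term of the ICC.

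The ICC form was chosen so that results carry over to other observers of similar skill. Such an observer's contour would not be inside the reference. The observer study is also where the plan tests whether readers place boundaries more consistently with the grid, and Section 9.2 still sizes the study on ICCs of 0.95, 0.9 and 0.8.

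**Working it through.** **1. The plan's own figure.** Inputs from Section 9.2: 32 participants; standard ICC 0.95, 0.9 or 0.8; increase 3.5%, 7.7% or 17%. From Section 9.4.1: k = 4 observers. For the average-rater ICC, F0 = 1/(1 - ICC), with 31 and 93 degrees of freedom at n = 32. Lower limit = 1 - F.975(31, 93)/F0; upper limit = 1 - 1/(F0 × F.975(93, 31)).

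| Standard ICC | Research ICC | 95% interval, standard | 95% interval, research | Smallest n without overlap |
|---|---|---|---|---|
| 0.90 | 0.90 × 1.077 = 0.9693 | 0.8283-0.9465 | 0.9473-0.9836 | 32 |
| 0.80 | 0.80 × 1.17 = 0.936 | 0.6566-0.8931 | 0.8901-0.9658 | 34 |
| 0.95 | 0.95 + 0.035 = 0.985 | 0.9142-0.9733 | 0.9742-0.9920 | 31 |
| 0.95 | 0.95 × 1.035 = 0.9832 | 0.9142-0.9733 | 0.9712-0.9910 | 37 |

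So 32 is reproduced closely if 3.5% is read as an absolute increase. The planning ICC is consistent with the four-observer ICC of Section 9.4.7.

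**2. Direction of the part-whole effect.** Suppose four independent errors with variance s² and a simple mean as consensus. The variance of an observer's deviation is s²(1 - 1/4) = 0.75s² with the own contour in the mean, s² against the truth, and s²(1 + 1/3) = 1.33s² against the mean of the other three. The SD factors are 0.87, 1 and 1.15. Self-inclusion is too favourable by about as much as leave-one-out is too harsh.

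**3. STAPLE.** Simulation A has 32 participants, four observers, smooth random contour errors on a disc, CI as overlap over union, and ICC(2,k) = (MSR - MSE)/(MSR + (MSC - MSE)/n). Assumed, because the documents give no values: error SD as a share of the radius, and log-SD, the between-participant SD of log contour error. Cells show mean CI / ICC of CI.

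| Error SD, log-SD, STAPLE region | Own contour in | Leave-one-out | True contour |
|---|---|---|---|
| 4%, 0.5, box | 0.949 / 0.38 | 0.927 / 0.83 | 0.937 / 0.79 |
| 4%, 0.5, whole image | 0.951 / 0.43 | 0.929 / 0.83 | 0.942 / 0.74 |
| 10%, 0.4, box | 0.886 / -0.06 | 0.838 / 0.78 | 0.860 / 0.65 |
| 10%, 0.4, whole image | 0.879 / 0.16 | 0.825 / 0.81 | 0.856 / 0.64 |

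Self-inclusion exceeds the true-contour mean by 0.012, 0.009, 0.026 and 0.023. Leave-one-out falls below it by 0.010, 0.013, 0.022 and 0.031. An observer scored a CI above 0.995 in 16%, 9%, 6% and 3% of participants with self-inclusion and in none otherwise, which is the capture effect. For HD the ICC falls less: 0.56-0.72 with self-inclusion, 0.86-0.89 leave-one-out, 0.80-0.83 against the true contour. With a mean-contour consensus the ICC of CI is essentially unchanged (0.83 against 0.84), so the fall comes from STAPLE's weighting.

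**4. Dependence on heterogeneity.** In simulation A, the ICC of CI falls from 0.74-0.76 (leave-one-out) to below zero at log-SD 0.25, from 0.92-0.95 to 0.65-0.71 at 0.8, and from 0.95-0.96 to 0.74-0.76 at 1.0. Simulation B, run separately under its own assumed contour errors, gives about 0.36 against 0.77-0.81 for the true contour at log-SD 0.3, and 0.82-0.86 against 0.95-0.96 at 0.8.

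**5. Difference between scan types.** Simulation A, error SD 4% (research) and 8% (standard), log-SD 0.5:

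| Reference | Mean CI research / standard | Difference | Ratio of (1 - CI) |
|---|---|---|---|
| Own contour in | 0.950 / 0.902 | 0.048 | 0.050/0.098 = 0.51 |
| Leave-one-out | 0.928 / 0.860 | 0.068 | 0.072/0.140 = 0.51 |
| True contour | 0.939 / 0.881 | 0.058 | 0.061/0.119 = 0.51 |

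The difference with self-inclusion is 0.048/0.068 = 0.71 of the leave-one-out value, about 30% smaller. The error ratio is unchanged, and the standardised paired difference is 1.36 with self-inclusion and 1.28 with leave-one-out.

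**6. Does the ICC separate the scan types?** In the same setting, against the true contour, the ICC is 0.76 (research) and 0.75 (standard), although contour error is halved.

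**The case against.** Much of the case for leaving the text alone stands.

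- Section 9.4.7 compares ICCs, not mean CIs, so inflated means do not enter the stated decision rule. True, but the ICC does enter it, and the ICC is what STAPLE self-inclusion distorts.
- A reader might infer that the smaller CI gap means lost sensitivity. Step 5 does not support that; it is a change of scale.
- A reader might infer that the ICC must collapse and can never reach the planning range of Section 9.2. That depends on assumed heterogeneity. Simulation B reaches 0.82-0.86 at log-SD 0.8, and the fall is only partial for HD.
- A reader might infer that the plan's justification is the reverse of the truth. The plan claims an advantage over a single pooled index, which cannot carry an observer effect. No calculation here includes that index, so the claim is not refuted. It simply does not extend to self-inclusion.
- Leave-one-out is not the truth either. It errs in mean CI about as far in the other direction and widens the scan-type difference (0.068 against 0.058).
- The analysis is one of several examples, with the final choice left until after scanning (Section 9.4.7). The primary analysis (Section 9.4.2) uses image quality metrics, and the secondary one compares software with each observer, so neither has this problem.

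**Conclusion.** The concern holds in limited form. Self-inclusion is in the text. Under the assumed contour errors it overstates mean CI by about 0.01-0.03 relative to the true contour, and with four-rater STAPLE it lowers the ICC(2,k) of CI on which the scan types are to be compared. The fall is large when participants differ little and partial when they differ more. The direction was the same in every STAPLE scenario run. The sizes are not fixed, and the simulations differ at the same nominal log-SD (0.65-0.71 and 0.82-0.86 at 0.8).

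Removing self-inclusion alone would not make the ICC comparison informative. An ICC of agreement scores mainly reflects how much participants differ, as step 6 shows. The two CI definitions in Section 9.4.1 also describe different quantities and must be reconciled.

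The consequence is confined to an optional exploratory analysis. That Section 9.2 still rests the sample size on an ICC is a separate matter, which this change does not settle.

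**What to change.** In Sections 9.4.1 and 9.4.7:

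1. Score observer i against a STAPLE reference built from the other three observers, separately for each structure and scan type, for both CI and HD. Alternatively, use the direct observer-to-observer CI and HD. With four observers that gives 4 × 3/2 = 6 scores per structure and scan, and the model must then carry both observers of a pair.
2. State one CI definition and use it throughout.
3. Compare the scores between scan types directly with a paired mixed model: scan type as fixed effect, participant and observer as random effects. Report the ICCs as description, and do not rely on non-overlap of their intervals alone. Giving the ratio of (1 - CI) beside the difference would make the result nearly independent of the choice of reference (step 5).
4. Limit the statement that the approach improves the comparison of scan types to its advantage over a single pooled index.

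Cost: a wording change and four STAPLE runs in place of one, that is three extra per structure and scan. No new scans or contours are needed. Downside: each leave-one-out reference rests on three observers, so scores lie below those against a true contour, the absolute scan-type difference is somewhat overstated, and the ICC is slightly overstated because the references share contours. The report should say so.
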